Centre for Addiction and Mental Health
Centre de toxicomanie et de santé mentale

Study Title:

Testing the Effectiveness of a Brief, Peer Support Intervention to Facilitate Transition from
Psychiatric Hospitalization

Principal Investigator:

[name].

NCT Number:

NCT02946255

Date:

Aug 15, 2018

STUDY PROTOCOL
(Original - 01 August 2016)
(Version 2 – 11 January 2017)
(Version 3 – 13 March 2017)
(Version 4 – 26 April 2017)
(Version 5 – 13 July 2017)
(Version 6 – 04 August 2017)
(Version 7 – 26 September 2017)
(Version 8 – 15 August 2018)

Study Title: Testing the Effectiveness of a Brief, Peer Support Intervention to Facilitate Transition from Psychiatric Hospitalization

Principal Investigator: [name].

Institution: Centre for Addiction and Mental Health

Co-Investigators: [name] MD, [name] MSW, [name] Psy.D., [name] PSW

Graduate Student: [name] Candidate

Introduction

Goal:

The goal of this study is **to generate an effective, readily implemented intervention to support individuals with schizophrenia in transition to communities after lengthy hospital stays**. This is a topic of importance given that, in Canada, approximately 75% of people with schizophrenia have been hospitalized, 38% are readmitted within 1 year, and the average length of stay is 27 days^{1,2}. This rate of readmission is considerably higher than other mental illnesses, with the first month post-discharge highlighted as the period of greatest risk for poor outcomes such as suicide, disengagement from care, and readmission^{1,3,4}. Such outcomes reflect poorly aligned inpatient and outpatient sectors⁵, with few interventions articulated in the small and variable literature in this area⁶.

Objective and outputs:

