1. Welcome Basket Intervention: The Welcome Basket (WB) intervention is based in part upon the original model established in New Haven, Connecticut in 1996⁸. However, this version of the WB differs from the original in its brevity (original involved several months of follow up), use of 1-1 outreach (as opposed to group meetings), and employment of compensatory interventions. In the proposed study, Peer Support Workers (PSWs) hold 1-2 initial meetings with clients (typically 30-60 minutes) in the 2-week period before they are discharged from hospital. In these meetings they will describe the program and undertake an assessment of the individual's needs and interests as they pertain to their transition to the community. From this assessment the two core components of the intervention are initiated. First, a "welcome basket" is created based upon the assessment, containing staple supplies, plants, coupons for stores nearby the client's residence, and comfort items within a modest budget (for the purposes of this study the budget will be up to \$40/basket). The PSW also forms a plan with the client about tours of their neighbourhood to familiarize them with the local resources (e.g., low cost entertainment venues; libraries; parks; inclusive spaces) and support them as needed in building confidence in accessing their local communities. These activities will take place through weekly visits (typically 2 hours/visit) in the 4 weeks immediately following discharge. WB will be provided in combination with core Cognitive Adaptation Training (CAT) compensatory interventions¹⁴. These include the setting up and placement of a calendar, lists of daily activities, signs that prompt recall of tasks, basic organization of living space, and the use of alarms and reminders (CAT supply budget of \$25). These supports are important (and often overlooked) in many clients' efforts to establish self-sufficiency after many weeks and months in hospital where staff typically initiate and structure the majority of activities.

participants who received the WB, we observed staff and client qualitative reports of successful implementation and outcome. We also observed significant quantitative changes in community functioning (ES = 0.64), domains of quality of life (ES = .38 – 1.28), psychological community integration (ES = .51) and a trend of lower rehospitalization at 6 months post-discharge as compared with average readmission rates on referring units.

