2. Welcome Basket (Brief) Intervention: The brief version of the Welcome Basket (WBbr) was developed based upon the observation in feasibility testing that for some participants much of the benefit of this approach appeared to be centred upon the visits immediately prior and subsequent to discharge. In the WBbr the same core components will be present, albeit in an abbreviated form with one 30-60 minute visit in the week prior to discharge and a single, 3-hour visit in the week subsequent to discharge in which the welcome basket would be delivered, core CAT strategies discussed and implemented, and some basic orientation to community resources undertaken. This brief version of the intervention has not to date been studied.

Treatment As Usual

Treatment as usual (TAU) involves the typical discharge procedures for clients from Unit 2, Forensic and EPU wards at CAMH. It includes referral to outpatient psychiatric services and relevant community supports with the transition facilitated by inpatient social work staff.

Controlling for Case Management

It will be a requirement that all clients enrolled in the study are engaged in some form of community-based case management along with medical follow-up. This strategy will assist in controlling for outcome variance impacted by conditions other than the intervention being studied.

Peer Support Worker Training and Clinical Context

Inpatient and outpatient clinicians and administrators are familiar with the intervention and regarded it positively from feasibility testing through to its current, ongoing delivery. There are currently 5 Peer Support Workers on staff who are extensively trained in the WB intervention. They were initially trained by [name] who developed the original WB intervention in New Haven and were trained in compensatory intervention by CAT specialists in collaboration with Drs. [name] and [name].

Participant Allocation and Blinding

For the trial, blocked randomization at a 2:2:1 ratio (TAU:WB:WBbr) will be employed to ensure balance in sample size between treatment and control groups. Stratification will not be employed as feasibility study findings did not suggest significant variance attributable to demographic or treatment history factors. Study measures will be collected by research assistants blinded to the treatment condition.

3. What are the planned inclusion/exclusion criteria?

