analyzed using mixed-effects linear modeling. For these analyses, a time effect will reflect changes across groups over time, and the group-by-time interaction will reflect changes over time between the groups. For all analyses $p < .05$ will be used as the level of significance with Cohen's d effect sizes reported. A blinded interim analysis will be conducted to determine if the sampling estimation needs to be revised. Plotting, mean and variance estimates will be calculated using the data from the WB brief treatment arm and compared with the control and full treatment.

All interviews will be recorded and transcribed by the graduate research assistant and undergraduate volunteers. Two independent researchers will code the transcripts using thematic content analysis²⁵, in order to analyze common themes that occur within the data. The PI will resolve any discrepancies that occur within the qualitative analysis. The themes will be brought back and discussed with the peer workers and WB team. Any other comments or themes that arise from this discussion will be documented using field notes²⁶.

6. Data Management and Integrity

The basic protection against risk in this study will be provided by [name] (study PI). The PI will have primary responsibility for monitoring of participants during the entire time they participate in the study. The PI will meet regularly with study personnel to review accrued data, data confidentiality, and adherence to protocol design, recruitment, and participant complaints. During meetings the Study PI will also review the enrollment data, the accrual and integrity of clinical data, and any adverse event associated with the various components of the study. If a serious adverse event occurs during the study, it will be reported to REB.

All data pertaining to a participant's involvement in this study will be coded and stored in locked offices. This information will only be accessible to the research team. In unusual cases, a participant's research records may be released in response to a court order. If the research team learns that a participant or someone with whom the participant is involved with is in serious danger or harm, an investigator will inform the appropriate agencies as per legal or regulatory requirements.

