Following provision of written informed consent, all participants will be assessed for suitability for inclusion in the study based on the inclusion and exclusion criteria. If it is deemed necessary, research staff may review participants' CAMH medical charts to obtain additional information to confirm their eligibility or to obtain clinically relevant information for research purposes and the contact information of their case manager. The study team will also have access to the participant's health records in order to document their participation in this study into their CAMH health record. The investigator or research staff may also request information from the participant's physician and/or a member of their case management team after obtaining consent for release of personal health information to determine eligibility.

Ongoing experience with the delivery of this intervention over the past 3 years has resulted in both confidence that this study will not run into substantive challenges as well as knowledge of an array of problem mitigating strategies. Recruitment has at times slowed, though this has historically been addressed readily through meeting with managers who in turn encourage teams, engagement of the Social Work practice group, and presenting at team meetings. In this period there have been no adverse events in the delivery of this intervention, it has proven feasible, and outcomes associated with its delivery have been positive.

Additionally, as part of the CLEARR (Clinical Engagement and Research Recruitment) initiative, a delegated Research Coordinator under the supervision of a CLEARR team recruiting clinician and accountable to the Research Manager will identify potential participants and notify the research team and the participant's clinician about their eligibility to participate in the study. The clinician will then ask their client if they would be willing to meet with a study team member about participating. Only with clients' agreement will they be approached.

The delegated Research Coordinator will access personal health information (PHI) in I-CARE in order to determine eligibility of CAMH clients to participate in the research study. No PHI except MRN will be collected for this purpose and this information will be kept in a secure locked location per Research Standard Operating Procedures SOP# CR501.

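### Adverse-event review is tied to study components, with no stated way of finding events, so events other than rehospitalization would be detected unequally across arms

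*Combined protocol and SAP*

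**What the plan says.** The safety provisions are a few sentences in Section 6 (Data Management and Integrity).

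- Oversight: "The PI will have primary responsibility for monitoring of participants during the entire time they participate in the study".
- Review at meetings: the PI looks at enrolment, data integrity and "any adverse event associated with the various components of the study".
- Serious events: "If a serious adverse event occurs during the study, it will be reported to REB". This carries no limit by arm or by relation to the study.

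The document contains no definition of an adverse event, no form or set questions, no time at which anyone is asked, no rule for judging relatedness and no table of events by arm.

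The Introduction (Goal) explains why the period matters, with "the first month post-discharge highlighted as the period of greatest risk for poor outcomes such as suicide, disengagement from care, and readmission". In Section 2, WB provides "weekly visits (typically 2 hours/visit) in the 4 weeks immediately following discharge", WBbr provides "a single, 3-hour visit in the week subsequent to discharge", and TAU is the usual discharge process with no peer visit. Every participant must have case management and medical follow-up. Section 1 schedules assessments for all arms at 4 weeks and 6 months after discharge, and Section 2 has research assistants collect the measures blind to arm.

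**The concern.** Two features work together.

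**Attribution comes before counting.** The meeting review takes in events already judged to be connected with a study component. A TAU participant receives only the assessments, so few non-serious TAU events could qualify, whatever their true frequency.

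**The chance of hearing about an event depends on the arm.** Study staff visit WB participants weekly in the month of highest stated risk. They visit WBbr participants once and TAU participants not at all. The serious-event sentence is a duty to report; it does not say who asks, when, or from what source. A serious event must still come to light before it can be reported.

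Any published adverse-event count, or a statement that none occurred, would then partly reflect who was visited. This matters most for self-harm and death, because suicide is among the outcomes the protocol uses to justify the intervention.

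**Working it through.** **1. Arm sizes.** Section 5 gives 125 participants at 2:2:1 (TAU:WB:WBbr).
- 125 × 2/5 = 50 TAU, 50 WB; 125 × 1/5 = 25 WBbr.
- With 13% attrition: 50 × 0.87 = 43.5 and 25 × 0.87 = 21.75. These reproduce the plan's 44, 44 and 22 completers.

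**2. Study-delivered contact after discharge, up to week 4** (Sections 1 and 2).

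| Arm | Peer visits per participant | Hours | Peer visits in arm | Week-4 assessment |
|---|---|---|---|---|
| WB | 4 | 4 × 2 = 8 | 50 × 4 = 200 | 1 |
| WBbr | 1 | 1 × 3 = 3 | 25 × 1 = 25 | 1 |
| TAU | 0 | 0 | 0 | 1 |

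The assessment is common to all arms. The imbalance lies in the visits before it.

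**3. What is already collected alike in every arm** (Section 4).
- Rehospitalizations and length of stay at 4 weeks and 6 months, from case managers, with a database check for CAMH admissions.
- Service use, and symptom scales (the Brief Symptom Inventory and the GAIN Short Screener).
- Hospitalization and symptomatology are also among the variables that Section 5 compares between WB and TAU.

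**4. What is left without a stated arm-neutral route.** No listed measure is specified to record a suicide attempt, self-harm or a death without admission. Case managers are asked for the community-functioning ratings and rehospitalization; no section asks them for adverse events. The withdrawal reasons in Section 7 include loss to follow-up but do not mention death, so a death might appear only as a drop-out.

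**5. Illustration of unequal detection.** The document gives neither event rates nor capture rates, so all inputs here are assumptions: the same true risk p in both arms, 50 per arm, capture c(WB) = 0.90, and c(TAU) = 0.70, 0.50 or 0.30.
- Expected recorded events = 50 × p × c. Apparent ratio = c(WB)/c(TAU), whatever p is.
- At p = 0.20, WB records 50 × 0.20 × 0.90 = 9.

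| c(TAU) | TAU events recorded | Apparent WB:TAU ratio |
|---|---|---|
| 0.70 | 7 | 1.29 |
| 0.50 | 5 | 1.80 |
| 0.30 | 3 | 3.00 |

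With equal capture the expected ratio is 1.0. The direction assumes that weekly visits reveal more events.

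**The case against.** The strongest reply is that most of what matters is already covered. Serious events are reportable from any arm. All arms have the week-4 assessment and required case management. Readmission, the most readily counted of the three named risks, is collected the same way throughout and compared. Service use may pick up emergency visits, although the document does not name them. No between-arm adverse-event analysis is planned, so the plan itself produces no biased ratio. All of this stands, and it rules out several stronger readings that a reader might infer:

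- *That TAU has no scheduled contact in the first month.* It has the week-4 assessment and case management. Only the study-delivered visits before that assessment differ.
- *That serious TAU events are excluded.* The serious-event sentence has no such limit. The attribution wording governs the PI's review, and serious events keep their REB route.
- *That the trial cannot address first-month harms at all.* Readmission and symptoms can be compared between WB and TAU.
- *That past experience shows events being filtered out.* Section 7 says "In this period there have been no adverse events in the delivery of this intervention", and Section 2 mentions rehospitalization among feasibility participants. But Section 2 gives only a trend against unit averages, and the Section 7 remark describes earlier service delivery, not this trial's rule. Nothing shows that events were discarded.

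It is also fair to say that "any adverse event associated with the various components of the study" is loose wording and may have been meant more broadly, and that completed suicide could not be compared informatively at 50 per arm under any rule. Neither point supplies a method for finding events.

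**Conclusion.** The concern holds for events other than rehospitalization. As written, their detection would differ by arm through attribution and through 4, 1 or 0 study-delivered visits before week 4. Adverse-event counts, or a statement of none, should not be read as comparable between arms. Rehospitalization, service use and symptoms are not affected, and neither is the primary comparison on community functioning.

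The size cannot be derived from the document. The range of 1.3 to 3.0 rests wholly on the assumed capture rates and shows only that the distortion could be material. The conclusion further assumes that peers pass on what they learn during visits, and that case managers are not separately asked about such events, since no section says they are. This is an inexpensive gap worth closing, not a flaw that undermines the trial's main result.

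**What to change.** 1. Reword the Section 6 review so that adverse events are recorded in all three arms regardless of relation to the study. Record relatedness afterwards as an added column, not as a condition of entry.
2. At the existing week-4 and month-6 interviews, ask participants and case managers the same short list in every arm: death, suicide attempt or self-harm, emergency visit, and other serious event, each with its date.
3. Summarise these descriptively by randomised arm, from this source only, and show the number of missed interviews per arm.
4. List events that peers report spontaneously in a separate table, outside the between-arm summary. Leave REB reporting of serious events unchanged.

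The cost is a protocol rewording, a few extra questions at interviews that already take place, and more events to tabulate, many of them unrelated to the intervention. Some events will be lost where an interview is missed. At the plan's 13% attrition that is about 50 × 0.13 = 6.5 participants in each of WB and TAU, and 25 × 0.13 = 3.25 in WBbr, which is why the missed-interview counts belong beside the table.

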3. What do you perceive is your role in the intervention?
4. What do you perceive is the client's role in the intervention?
5. What do you hope to achieve when you are working with WB clients?
6. How does the WB intervention create or sustain changes in clients? Probe: challenges, barriers.
7. What is the role of the person's context in the intervention and how does that affect the effectiveness of the intervention? (e.g., gender, ethnicity, housing, etc.)
8. What are some challenges that occur when you are working with WB clients?
9. How have you resolved these challenges?

Role as a Peer Support Worker in WB

10. How has being in the WB program affected your position as a peer support worker?
11. What are the strengths/challenges of working within a research and RCT format?
12. How is the WB different from other peer support interventions you have been involved with?
13. What are the strengths/ weaknesses of the WB?
14. What system level barriers have you run into as a peer worker while working on the WB project?
15. How have you resolved these challenges?

Implementation of WB

16. How do you carry out the logistics of the WB (e.g., money, travel, etc.)
17. How do you create connections with inpatient/outpatient teams in order to carry out the intervention successfully?
18. How have issues with power within the team/hospital been handled?
19. How is peer support within the hospital context different than community?
20. What implementation barriers have you run into while working on the WB project?
21. How have you resolved these challenges?
22. Where do you think peer support is going?
23. Are there any other considerations that need to happen? How would you do this differently?

Budget

Budget Justification (Total \$259,598 – 3 years)

Personnel (Subtotal: 226,229)

Staff will include (i) one 1.0 FTE research assistant who will manage data, communications, and collect data (135,581; 3 years – includes 30% benefits), (ii) two 0.5 FTE Peer Support Workers to deliver the intervention, with both providing 50% of both brief and full versions of the WB to offset clinician effects (one at 69,167 in grant and one at 69,167 in-kind (core funded, CAMH), 2 years to allow for preparation, delivery, and wind down along with capacity building/KTE), and (iii) 4k for 35 hours of statistical consulting at \$120/hour (Biostatistician). Peer Supports will carry caseloads of 4-6 participants each. Along with outreach travel, supply purchase, documentation, and assistance with recruitment (e.g., orienting teams, connecting with social workers) this workload aligns with our past experience with the intervention.

(Research Analyst 2, step 2, (Y1 29.27 + 30% bens 8.78 = 38.05 (.8fte, 10mos 45,660); Y2 29.71 + 30% bens 8.91 = 38.62 (.8fte 55,613); Y3 30.16 + 30% bens 9.05 = 39.21 (.8fte – minus 1 month, 51,789)

Peer Support Worker (Y1 27.08 + 30% bens 8.12 = 35.20, total 68,640; Y2 27.49 + 30% bens 8.25 = 35.74, total 69,693)

Trainees (Subtotal: 18,604)

One graduate student trainee will be engaged for 2.5 years of the project (7 hours/week; 19.38/hour – includes 13% benefits; 18,604 total) who will assist with data entry and management, data collection, and work closely with the PI and the Research Assistant. Deliverables for the graduate student will be 1 poster for which they will be first author and authorship on the core peer-reviewed publication.

Consumables (Subtotal: 10,265)

At \$65/participant for WB intervention supplies, the total cost will be \$8,625. Participants will be reimbursed \$25/assessment (3 assessments/participant, 110 completers and 15 drop outs, total is \$4,250). A total of \$500 requested for general materials (printing, files, encrypted memory stick). A total of \$1,140 is requested for transit tokens for outreach by Peers (estimated 350 trips/\$3.25/trip).

Knowledge Translation (Subtotal: 4,500)

We are requesting \$2500 to fund the open access publication of the main paper to come out of the study. We are requesting \$2000 to cover the costs of the PI presenting the findings at an appropriate national or international meeting (estimated \$500 flight, \$50 per diem for 3 days, \$250/night hotel, \$200 taxi, \$500 meeting registration).
